#### **Post-operative instructions**

All patients will be instructed to maintain a liquid diet for 2 weeks after the sinus surgery, continue on a soft diet for one month and general diet for the remaining duration of the healing phase. If a patient presents with a removable prosthesis, the prosthesis will be evaluated for proper tissue adaptation. If the tissue adaptation is poor, the prosthesis will be relined using a soft reline material (GC Reline Soft, GC, Alsip, IL) following the surgery. The patient will be advised to avoid nose blowing and placing any undue pressure on the surgical site. The patient will be instructed to rinse gently with 0.12% chlorhexidine gluconate solution (Peridex) for the first two weeks following the surgery. Recall examinations will be scheduled two weeks following the surgery for suture removal and at 1, 3, and 6 months after sinus augmentation and 2 weeks before biopsy and implant placement. The biopsy and implant placement procedure will be performed 8 months after the grafting procedure. A CBCT scan will be taken 2 weeks before implant placement to determine the final implant position and size. (The post operative CBCT scan after sinus augmentation and prior to implant placement is standard protocol )

#### Surgical and post-operative complications

Surgical and post-operative complications such as perforation of the sinus membrane, acute or chronic sinus infection (pain, suppuration, swelling, nasal fluid leakage), bleeding, wound dehiscence, and exposure of the graft will be recorded.

#### **Biopsy Procedure:**

- After 8 months of healing, a full-thickness flap will be reflected and previous antrostomy site will be located using the same surgical template. Two trephines (2.75mm internal diameter and 3.5mm external diameter, ACE Surgical Supply Company, Inc., Brockton, MA) will be used to collect at least 8mm length biopsy specimen. Two cores will be taken from each patient site; one core from the previous lateral window of each sinus augmentation site without interfering with implant placement and one core from the implant osteotomy site. When obtaining the core from the implant osteotomy site, at least 8mm in length of the grafted bone will be included in the core. The trephines are marked at 8mm,10mm,13mm,15mm. The core samples will be kept in the trephine in 10% buffered formalin, coded and mailed to the laboratory for the histomorphometric analysis.
- 2. The alveolar ridge will be prepared for implant placement, in accordance with the conventional surgical protocol, and implants of appropriate dimensions will be placed.

Immediately after insertion the stability of the implants will be recorded by measuring the ISQ values.

- 3. Post-operative care instructions will be provided as described previously.
- 4. Appropriate healing time for the implants will be allowed for osseointegration, and definitive restorative prostheses will be constructed accordingly.

#### Histology / MicroCT assessment

The trephine with the retrieved specimens will be placed in 10% neutral buffered formalin. Each specimen will be labeled and packaged in an individual container, which will then be numerically coded to keep the patient's information confidential and examiners will be blinded. Specimens (40) will be sent to the Hard Tissue Research Laboratory, University of Minnesota School of Dentistry for histomorphometric analysis. Or the specimens will be analysed by using a MicroCT at the university of Loma Linda, center for radiation research. The microCT will give us digital reconstruction of the 3D structure of the core material. This will be analysed for new bone formation, amount of graft material remaining, interaction between the graft and the patient's native bone.

# Non-decalcified histologic processing and histomorphometric analysis include the followings:

-Dehydration and infiltration with resin.

-Retrieval of the core specimen from the trephine with as much care as possible at a specific point during infiltration with resin.

-Embedding in specialized Kulzer 7200 light polymerizing resin.

-Preparation of slides to  $45-50 \ \mu m$ .

-2 slides will be made from each of the core specimens unless there are extenuating circumstances for a specific specimen making it possible to only produce one good slide.

-Slides will be cut in a longitudinal section unless cross sections are requested.

-Staining of the slides.

-The specimen slides will be stained with Stevenel's blue and Van Gieson's picro-fuchsin. This stain differentially stains material within the specimens. Precise determinations of the percentage of vital, non-vital bone and non-bone components will be conducted using computerized image analysis.

15

-Vital bone stains bright red with variations in intensity depending on the maturity of the bone.

-Non-vital bone and osteoid stain bright green.

-Nuclei of cells, including osteoblasts, osteoclasts and osteocytes, stain blue.

-Connective tissue stains various shades of green.

-Non-biologic materials such as ceramic material, hydroxyapatite, membranes, etc., are not affected by the stain and are easily visualized and analyzed.

Two slides will be prepared from each core. Specimens will be cut vertically through the center of the core.

#### Histomorphometric analysis:

All the specimens will be digitized at the same magnification using a NIKON ECLIPSE 50i microscope (Nikon corporation, JAPAN) and a SPOT INSIGHT 2 mega sample digital camera (Diagnostic instruments Inc, USA). Histomorphometric measurements will be completed using a combination of SPOT 5.1 Advanced Software (Diagnostic instruments Inc, USA) and Adobe Photoshop (Adobe Systems, Inc.).

The measurements to be obtained and presented in tabular form are:

- 1. Percentage of the area of the core, which is bone. Of the bone, the percentage of vital and non-vital bone will be determined.
- 2. Percentage of non-bone material. (ABBM)
- 3. Percentage of connective tissue.

The histomorphometric data for each specimen will be recorded as the average of the 2 slides from the specimen.

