#### **Clinical Procedure:**

#### **Diagnosis and Treatment Plan**

- 1. Subjects will be informed in detail about the sequencing of the events that would take place during the study. This will include risks, benefits and alternatives for treatment.
- Preliminary impressions will be made with polyvinyl siloxane impression material (Exafast, GC America Inc., Alsip, IL). Diagnostic casts will be fabricated in type III dental stone (Microstone, Whip Mix, Louisville, KY).
- 3. The diagnostic casts will be articulated with the use of a face-bow on a Panadent semiadjustable articulator (Panadent Corporation, Colton, CA) using interocclusal record made with polyvinyl siloxane (Exabite, GC America Inc., Alsip, IL) and wax record bases.
- 4. The diagnostic waxing of the missing teeth will be fabricated with tooth-colored wax (Pro-Art, Ivoclar Vivadent, Inc., Williams, Amherst, NY), and then will be duplicated in type III dental stone for partially edentulous patients. In case of completely edentulous patients, denture teeth will be set up in an optimal position on a base plate based

on the conventional complete denture fabrication. A silicone lab putty (Polysiloxane Coltene Lab-Putty, Coltene Whaledent Inc. Cuyahoga Falls, OH) impression will be taken of this denture setup.

- 5. A vacuum-formed radiographic template (Polypropylene Coping Sheet, Ultradent Products, South Jordan, UT) with auto-polymerizing acrylic resin (Jet, radiopaque teeth color, Lang Dental, Wheeling, IL) will be fabricated from the duplicated cast for partially edentulous patients. For completely edentulous patients, a radiographic template will be fabricated from the silicone putty impression with radiopaque color auto-polymerizing acrylic resin for teeth and clear color for the base (Jet, radiopaque teeth color, Lang Dental, Wheeling, IL). These templates will be used in conjunction with the cast for identifying the desired locations of the dental implants.
- 6. All patients will undergo radiographic evaluations before sinus augmentation. A conebeam computed tomography (CBCT) scan (NEWTOM full volume scan of the maxilla) would be taken with the radiographic template. (The radiographic evaluation prior to sinus augmentation is standard protocol)

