#### **Surgical procedures**

 On the day of surgery, the patient will be asked to rinse their mouth with 0.12% chlorhexidine gluconate solution (Peridex) for 3 minutes prior to the surgery. After being seated, the patient will be monitored for blood pressure, pulse rate, and oxygen level and circumoral area will be scrubbed with a Povidone-Iodine swab stick (Aplicare, Aplicare Inc., Branford, CT) and the patient will be draped. Oxygen will be provided to the patient through the nasal cannula at a minimum rate of 3 liters/minute, if the patient chooses to be sedated.

- 2. All the patients will be treated with the same surgical technique consisting of sinus floor augmentation via a lateral approach. All surgeries will be performed by one surgeon (SU). After appropriate local anesthetic administration (2% Xylocaine with epinephrine 1:100,000, Dentsply International Inc., York, PA) administration, a midcrestal incision will be made and a vertical releasing incision will be made anteriorly at the appropriate location. A full-thickness flap will be reflected to expose the lateral wall of the sinus.
- 3. Each antrostomy will be outlined with a round carbide bur (KOMET USA, Rock Hill, SC) ensuring that the inferior border will be at least 2 mm superior to the sinus floor. If the lateral bone window is not completely separated from the surrounding bone, a mallet and chisel (H & H Company, Ontario, CA) will be used to facilitate complete separation.
- 4. Sinus membrane will be carefully elevated to create space for the bone graft. The bony remnant from the window will be elevated with the sinus membrane to form the roof of the future space for the bone graft material. The membrane's integrity will be checked visually and with the Valsalva test. If a perforation to the sinus membrane occurs, the surgeon will evaluate the site prior to proceeding. If the perforation is < 5 mm in diameter and is able to be repaired, the perforation will be isolated and a resorbable collagen membrane (Bio-Gide, Geistlich, Wolhusen, Switzerland) will be placed over the area, in such a position so as to overlay unaffected membrane by at least 3 mm in all directions. Then, the surgeon will continue with the procedure as

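### Bone is measured over the whole core with no graft-only region, so native ridge, very likely present in the implant-osteotomy core, counts as outcome and dilutes the material contrast there

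*Combined protocol and SAP*

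**What the plan says.** The Objective and Null Hypothesis sections set the target as new bone formed after augmentation with either of two bovine minerals. The Histomorphometric analysis section lists three measures. The first is "Percentage of the area of the core, which is bone", then broken down into vital and non-vital bone. The other two are the percentages of ABBM and of connective tissue. No region of interest, graft boundary or exclusion of residual ridge is given there.

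The Biopsy Procedure section takes two cores per site, described as follows: "one core from the previous lateral window of each sinus augmentation site without interfering with implant placement and one core from the implant osteotomy site". For the second it adds: "When obtaining the core from the implant osteotomy site, at least 8mm in length of the grafted bone will be included in the core". It also says: "The trephines are marked at 8mm,10mm,13mm,15mm". On sectioning, the histologic processing section says: "Slides will be cut in a longitudinal section unless cross sections are requested".

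Under the alternative microCT route, the Histology / MicroCT assessment section says of the reconstructed core: "This will be analysed for new bone formation, amount of graft material remaining, interaction between the graft and the patient's native bone". It gives no rule for telling native bone from new bone.

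One part of the document, between the Biopsy Procedure and the Histology / MicroCT assessment sections, was not available for this review. It is not counted as silent.

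**The concern.** The quantity measured is not the quantity in the hypothesis. An osteotomy for an implant enters through the alveolar ridge, and a requirement that the core hold a minimum length of grafted bone makes most sense if it may hold something else too. The default section runs along the length of the core, so a ridge segment would lie on the measured slide. Native ridge can be vital, so the vital/non-vital breakdown does not remove it.

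Bone that was there before surgery would then count as outcome in both arms. In the osteotomy core this pulls the expected difference towards zero and shifts the bone and ABBM percentages away from their values in the graft. A finding of no difference between two similar bovine minerals would be harder to interpret, because part of it could come from the area measured.

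**Working it through.** **The plan's own figures.** The plan states no effect size, SD or power, so there is none to reproduce. The specimen count does reproduce: (10 + 10) sinuses × 2 cores = 40. Of these, 20 are osteotomy cores.

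**Inputs from the plan.** At least 8 mm of graft in the osteotomy core; trephine marks at 8, 10, 13 and 15 mm; 10 sinuses per arm; P < .05.

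**Assumed inputs.** Ridge length *r*, graft lengths of 8 or 11 mm, bone at 25% of graft area and 50% of ridge area, and ABBM at 30% of graft area. The marks are depth marks, not planned core lengths; here they serve only to bound the core at 15 mm.

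**Dilution.** On a lengthwise section of even width, area share equals length share. With graft length *g*, the graft share is w = g/(g + r), and core bone % = w × graft bone % + (1 − w) × ridge bone %. If ridge bone and *w* do not depend on arm, the ridge term cancels in expectation and the core difference is w × the graft difference.

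| Graft (mm) | Ridge (mm) | Core (mm) | w | Bone 25% reads | ABBM 30% reads |
|---|---|---|---|---|---|
| 8 | 2 | 10 | 0.80 | 30.0% | 24.0% |
| 8 | 5 | 13 | 0.62 | 34.6% | 18.5% |
| 8 | 7 | 15 | 0.53 | 36.7% | 16.0% |
| 11 | 1 | 12 | 0.92 | 27.1% | 27.5% |
| 11 | 2 | 13 | 0.85 | 28.8% | 25.4% |
| 11 | 4 | 15 | 0.73 | 31.7% | 22.0% |

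First row: w = 8/10; bone (8 × 25 + 2 × 50)/10 = 30.0; ABBM 8 × 30/10 = 24.0.

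**Chance imbalance.** The ridge term cancels only on average. With 8 mm of graft and identical materials, mean ridge of 3 mm in one arm and 4 mm in the other gives (200 + 150)/11 = 31.8% against (200 + 200)/12 = 33.3%, a spurious 1.5 points. It can go either way.

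**Power, as illustration only.** A simulated two-sample t-test used 10 per arm, graft bone 25% against 35% with SD 8, ridge bone 50% with SD 8, and ridge length uniform over the stated range. Results for the osteotomy core:

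- Graft-only region: 75% power, mean difference 10.0 points.
- 8 mm of graft, ridge 1–7 mm: 61%, 6.8 points.
- 8 mm of graft, ridge 1–4 mm: 69%, 7.7 points.
- 11 mm of graft, ridge 1–4 mm: 72%, 8.2 points.

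For 8 mm of graft with ridge 1–7 mm, moving ridge bone from 30% to 70% moves power from 65% to 50% and leaves the 6.8 points unchanged. With no true difference, rejection stays at 4.9% to 5.1%. Power falls less steeply than the contrast because graft-related variation shrinks by the same factor.

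**The case against.** The strongest reply is that native bone in the core is inferred and its amount unknown. The plan gives neither residual ridge height nor intended core length. The factors 0.62 and 0.53 need graft at exactly the 8 mm floor, whereas the plan asks for at least that. This stands: those are unfavourable cases, and 11 mm of graft gives 0.92 to 0.73.

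Second, the plan gives partial protection. It secures a minimum graft content and takes a second core from the former lateral window, which is less exposed. Data are recorded per specimen, and only the two slides within a specimen are averaged, so the two core types can be reported apart from data already planned. This also stands, and it confines the point to the osteotomy core.

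Third, the laboratory might separate the tissues anyway, since the stain's intensity varies with bone maturity. No visible section says so or turns this into a native/new rule. ANCOVA is no remedy either: no covariates are named, and adjusting for ridge length would not by itself restore the diluted contrast.

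Two stronger readings should be resisted. A reader might infer that the microCT route already measures native and new bone separately. The text mentions native bone only in its interaction with the graft, without saying in which core or how it would be separated. A reader might also count the raised window as a second source of native bone, since "The bony remnant from the window will be elevated with the sinus membrane to form the roof of the future space". Nothing shows that either core reaches that roof or that the remnant is vital at 8 months, so the point does not rest on it.

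**Conclusion.** The concern holds for the implant-osteotomy core. Followed as written, the plan reports bone of any origin over the whole core, while the hypothesis concerns new bone in the graft. In expectation the material difference in that core is multiplied by graft length over core length: illustratively 0.80, 0.53 at worst within the trephine marks, and 0.92 to 0.73 with more graft. The bone percentage is overstated if ridge is denser than graft, and the ABBM percentage is understated. This rests on ridge being present, which is a strong inference, and on ridge bone and graft share not differing systematically by arm. In a single trial of 10 per arm, uneven ridge length can shift the difference in either direction.

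A reader might go further and infer a badly underpowered trial, inflated false positives, or dilution of all 40 specimens. The documents do not support these. This is a self-described pilot with no power target, the power figures depend on assumed inputs, type I error is unaffected, and half the specimens come from the less exposed site. The harm is mainly to what the estimate means. The change is worth making, with medium confidence in its practical size.

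**What to change.** In the Histomorphometric analysis section, define the bone, ABBM and connective tissue percentages for the osteotomy core over the grafted region only, excluding native ridge. Use the same region if microCT is chosen.

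- Have the blinded examiner mark the graft/native boundary by a written rule fixed before any slide is read.
- Do not let the rule rest only on where graft particles end: the materials may resorb differently, and the region could then differ by arm. The pre-operative CBCT can guide ridge height, since "All patients will undergo radiographic evaluations before sinus augmentation".
- Report osteotomy and lateral-window cores separately.
- Report, by arm, the native length and how often the boundary could not be identified.
- Show whole-core percentages as a sensitivity result, so that no core drops out of the report.

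The cost is marking up to 40 slides (20 osteotomy cores × 2 slides), or 20 microCT volumes, and a short amendment. Each percentage rests on a smaller area and is slightly less precise. Some boundary error will remain: 1 mm of native bone left with 8 mm of graft still gives 8/9 = 0.89. CBCT guidance is approximate, because no visible section describes marking core orientation or matching slides to the scan.

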#### **Null Hypothesis:**

There is no histomorphometric difference in new bone formation in maxillary sinuses augmented using two different materials, ABBM (Bio-oss) and ABBM (InterOss).

5

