#### **Statistical analysis:**

Statistical package for the social science (SPSS) version 21(SPSS®, IL) computer software will be used for descriptive and inferential statistics in all parameters. Descriptive statistics will be presented for each clinical parameter. Primary hypothesis will be analyzed if it is normally distributed. ANCOVA procedure will be used to test the relation between the primary variables and control the influences of the covariates. Statistical significance is denoted when P < .05.

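### The outcome is recorded per core, two cores per sinus, but the ANCOVA names no unit of analysis; if the 40 core values enter as independent rows, the 5% level is not controlled

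*Combined protocol and SAP*

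**What the plan says.** The hypothesis is about sinuses: "There is no histomorphometric difference in new bone formation in maxillary sinuses augmented using two different materials". The randomization paragraph, under Informed Consent, plans 10 sinus augmentations per group. It also makes each sinus of a bilateral patient a separate unit, but only for the purpose of randomization.

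The data come at a finer level. The Biopsy Procedure section states: "Two cores will be taken from each patient site; one core from the previous lateral window of each sinus augmentation site". The second is "one core from the implant osteotomy site", for which "at least 8mm in length of the grafted bone will be included in the core". The Histology / MicroCT section gives the total: "Specimens (40) will be sent to the Hard Tissue Research Laboratory". The Histomorphometric analysis section defines the first measurement as "Percentage of the area of the core, which is bone" and gives one rule for combining values: "The histomorphometric data for each specimen will be recorded as the average of the 2 slides from the specimen".

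The Statistical analysis section says "ANCOVA procedure will be used to test the relation between the primary variables and control the influences of the covariates" and sets significance at P below .05. It names no row of analysis, no rule for combining or choosing between a sinus's two cores, no list of covariates, and no term for sinus, patient or core location.

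**The concern.** The plan reduces slides to cores but never cores to sinuses. An analyst who takes the values in the form in which they are recorded has 40 rows, and a standard ANCOVA assumes that those rows are independent. Two cores from the same sinus share one patient, one operation and one graft, so they are likely to be correlated. The graft is allocated to about 20 sinuses, not to 40 cores, and the precision of the comparison is set by the sinuses.

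The two locations may also differ in mean. The osteotomy core has a minimum length of grafted bone, so it may contain native ridge as well (an inference; the plan does not say so), and the measurement is taken over the whole core area. A location difference left out of the model inflates the residual and pushes the error the other way.

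At stake is the meaning of the one significance test in the plan. Even a reader who takes the sinus as the unit still has to choose between the mean of the two cores, the lateral-window core and the osteotomy core, and the plan does not choose.

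**Working it through.** **Inputs from the documents.** 10 + 10 sinuses (Informed Consent, randomization paragraph); 2 cores per sinus (Biopsy Procedure); 40 specimens (Histology / MicroCT assessment); significance level 0.05 (Statistical analysis), taken as two-sided because sidedness is not stated.

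**Inputs assumed.** Within-sinus ICC ρ = 0.1, 0.3, 0.5, 0.7; difference d between the two location means = 0, 0.5, 1 or 1.5 core SD; no bilateral patients; no other covariates. The documents give neither ρ nor d.

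**Step 1: the plan's own count.** (10 + 10) × 2 = 40, which matches the stated number of specimens. With ρ = 0 and d = 0, a test on 40 rows gives a simulated error of about 5%, so the set-up reproduces the nominal level when its assumption is true.

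**Step 2: formula.** Let the core variance be 1. The true variance of an arm mean (10 sinuses, 2 cores each) is (1 + ρ)/20. A test on 40 independent rows without a location term estimates it as about (1 + d²/4)/20. In large samples the actual error is therefore

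α ≈ 2 × [1 − Φ(1.96 / √((1 + ρ)/(1 + d²/4)))].

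- ρ = 0.5, d = 0: √1.5 = 1.225; 1.96/1.225 = 1.60; α ≈ 11.0%.
- ρ = 0.5, d = 1.5: √(1.5/1.5625) = 0.980; 1.96/0.980 = 2.00; α ≈ 4.6%.

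**Step 3: simulation at the trial's size.** 200,000 null trials per setting; core value = sinus effect (variance ρ) + core effect (variance 1 − ρ), with d added at one location. Monte Carlo standard error is at most 0.08 percentage points.

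| Analysis | ρ = 0.1 | 0.3 | 0.5 | 0.7 |
|---|---|---|---|---|
| 40 rows, d = 0 (38 df) | 6.1% | 8.7% | 11.3% | 14.1% |
| 40 rows, location in model (37 df) | 6.1% | 8.6% | 11.0% | 13.7% |
| 40 rows, d = 0.5 omitted | 5.3% | 7.7% | 10.1% | 12.8% |
| 40 rows, d = 1 omitted | 3.6% | 5.4% | 7.3% | 9.5% |
| 40 rows, d = 1.5 omitted | 1.9% | 3.1% | 4.3% | 5.9% |

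One value per sinus (mean of two cores, or a single location; 20 rows, 18 df) gives 4.9% to 5.1% in every setting.

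**Step 4: mixed model.** With location fixed and sinus random (REML, zero variance dropped), the error is 4.4% at ρ = 0.1, where the sinus variance is estimated as zero in 34% of trials, and 4.9% at ρ = 0.3. This is slightly conservative at low ICC.

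**Step 5: interval width.** Sinus means against pooled cores, d = 0: roughly (2.101/2.024) × √(1 + ρ) = 1.09, 1.18, 1.27, 1.35. The simulated ratios are 1.08, 1.19, 1.28, 1.37.

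**The case against.** The strongest reply is that the inflated error belongs to an analysis that the plan does not specify. How a value is recorded does not settle what a row of the analysis is. One row per sinus with two core columns, or a separate ANCOVA for each location, fits the text as well, and a test on a single location holds 5%. The null hypothesis and the group sizes both point to the sinus. This stands in part. A reader might infer that the plan pools the cores; it does not say so, and the error figures apply only if that is done. But pooling is what results from a plain ANCOVA on the values as recorded, and nothing in the plan rules it out.

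The second reply is that the figures come from a chosen grid. This stands. Some combinations land close to 5% (for example 5.4% at ρ = 0.3 with a 1 SD difference omitted). Values beyond the grid go further: about 17% at ρ = 0.9 with d = 0, and about 0.5% at ρ = 0 with d = 2. A reader might infer that the trial's error is 14%, or that it is always too high. Neither follows; the level is uncontrolled.

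The third concerns bilateral patients. A reader might infer that two sinuses from one patient bias the sinus-level test. Under separate allocation of each sinus, the simulated error averages 5.0% with 1, 2 or 4 such patients (assumed correlation 0.5 within a sinus and 0.3 between a patient's sinuses). It departs from 5% only conditionally, when pairs happen to share a graft (5.5% to 6.9%) or to be split (4.6% to 3.4%). That does not justify dropping randomised sinuses from the primary test.

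Finally, this is titled a pilot. It still states a null hypothesis and a significance threshold, so the test needs a defined unit.

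**Conclusion.** The omission is certain in the public text: outcome values are defined per core, and no rule carries them to the sinus. The consequence is conditional. If the 40 values are analysed as independent rows, the two-sided error is about 6% to 14% for an ICC of 0.1 to 0.7 when the locations have equal means or location is in the model. It can drop to about 2% (ICC 0.1) when a 1.5 SD location difference is left in the residual. These figures rest on an assumed ICC and location difference, 10 sinuses per arm, two cores from every sinus, and no bilateral patients. They show that the nominal level is not assured; they do not estimate this trial's error. The point should be fixed before analysis.

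**What to change.** In the Histomorphometric analysis and Statistical analysis sections, state that the sinus is the unit of analysis and that the primary test uses one value per sinus. Name that value now: the mean of the two cores, or one core location chosen in advance. The mean describes a mix of two locations. A single location avoids that, at a standard error larger by √(2/(1 + ρ)), that is 35% / 24% / 15% / 8% at ICC 0.1 / 0.3 / 0.5 / 0.7. A mixed model with core location fixed and sinus random is an acceptable alternative.

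Also reconcile Patient selection (20 patients), the randomization paragraph (10 sinuses per group, bilateral patients allowed), Pre-operative procedure (patients assigned) and the count of 40 specimens. At two cores per sinus, 20 patients and 40 specimens leave no room for a bilateral patient. Report any bilateral patients, with a sensitivity analysis that accounts for the patient.

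The cost is a few sentences, by the written amendment that the Adherence to Protocol section requires, and no extra patients, biopsies or staff. With equal location means, intervals are about 8% to 37% wider than from pooled cores, which only removes false precision. If a 1 SD location difference would otherwise have been left out of the pooled model, the change is −4% to +21%.
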